Rapid reduction of sNVP with mirtazapine treatment has been reported in case series of pregnant persons^{17,18} who have not responded to other medications. These cases include mothers who requested terminations of desired pregnancies due to inability to tolerate sNVP. Reproductive outcomes for mirtazapine do not indicate an elevated risk for birth defects, although the number studied is relatively small (≈500). Medications commonly used to treat sNVP are first-line drugs; however, a substantial number of pregnant persons do not respond adequately and novel therapeutics are urgently needed.

Mirtazapine is a compelling candidate to expand therapeutic options for sNVP. This exploratory/developmental phase 2 project is designed to determine whether a Phase 3 randomized controlled trial (RCT) is warranted by establishing the acceptability, tolerability, dosing and safety of mirtazapine for sNVP. Mirtazapine is not approved by the FDA for treatment of nausea and vomiting of pregnancy (NVP); therefore, in this clinical trial, mirtazapine is an investigational product.

We will conduct a 3-week open trial of 25 pregnant persons who have not responded to at least two antiemetic drugs. We hypothesize that mirtazapine will exhibit satisfactory acceptability, tolerability and safety in pregnant persons with sNVP. After the initial trial, a continuation period or a mirtazapine tapering regimen with monitoring will be offered. The aims of the trial are:

1. Determine the acceptability of mirtazapine for sNVP that does not respond to two standard drugs.

2. Define the tolerability and safety of an escalating 3-week mirtazapine dose regimen.

3. Assess the duration of treatment required following the initial 3-week trial and the adequacy of a tapering regimen for persons who discontinue mirtazapine.

4. Determine pregnancy and neonatal outcomes for all enrolled persons. We will collect data on delivery outcomes only with the peripartum events scale

5. Explore the relationship of study drug dose and plasma concentration with side effects and pharmacogenetics by obtaining weekly plasma.

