Mirtazapine is prescribed for nausea and vomiting during cancer chemotherapy and preoperatively to prevent post-surgical nausea and vomiting. During pregnancy, rapid reduction of nausea and vomiting following mirtazapine treatment has been reported in case series of persons who have not responded to other medications. Mirtazapine impacts the serotonin receptor (similar to the anti-emetic drug ondansetron) as well as three additional receptors involved in the physiologic cascade that results in nausea and emesis. Reproductive outcome data for mirtazapine do not indicate an increased risk for birth defects, although the number of persons studied is relatively small (≈500). Additionally, pharmacogenetic factors that affect mirtazapine plasma concentrations and thereby affect its tolerability and safety will be considered in the proposed project.

Mirtazapine is a compelling candidate repurpose to expand therapeutic options for this disabling disorder. A total of 26 cases in of mirtazapine for sNVP have been published.^{17,18} These people did not respond to first-line drugs for sNVP (doxylamine/pyridoxine, ondansetron, metoclopramide, dimenhydrinate and promethazine). The mirtazapine dose ranged from 15-45 mg/day, with a modal dose of 30 mg/day. Response was rapid, with reduction of nausea on the first day of treatment.²⁸ In a recently published series of seven cases,²⁹ the mean gestational age at initiation was 11.6 weeks (range 7–14). The mean treatment duration was 9.1 weeks (range 4–24). Mirtazapine's antiemetic properties derive from multiple effects on the cascade of events that culminate in emesis^{30 31} which do not depend on its antidepressant effects. Mirtazapine adds therapeutic value by improving sleep and appetite. These actions of mirtazapine do not depend upon the presence of an underlying psychiatric disorder; however, people with unremitting sNVP often have depressive and anxiety symptoms secondary to stress and functional impairment.

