Both compliance with treatment and vomiting within an hour of the dose will be recorded in REDCap (along with the daily PUQE score) to evaluate these factors in the interpretation of

plasma concentrations. Mirtazapine treatment will continue unless the participant withdraws consent, experiences a limiting side effect or an obstetrician decides that the health risk to the patient compels discontinuation. At the end of the 3-week trial, subjects will be asked whether they prefer to continue mirtazapine, which will also serve as a measure of treatment satisfaction. Pregnant persons who choose to stop treatment will be given a taper regimen in reverse order of the dose escalation required for the 3-week trial. For example, if a patient is taking 45 mg at the end of week 3, she will begin a taper (by week) of 30 to 15 to 7.5 to 0 mg. If she relapses or has discontinuation symptoms, the previous effective dose will be given. She may attempt to taper again with the same approach. Participants who continue to be treated with mirtazapine in the continuation phase will be followed monthly throughout pregnancy unless they withdraw consent.

Maintenance Drug Treatment (Figure 4). For pregnant persons who choose to continue treatment, mirtazapine will be prescribed at the dose achieved at the end of the 3-week trial. The duration of treatment will be decided by the patient with a study obstetrician based upon her response and comfort with drug discontinuation. These data will be novel since no information on the duration of treatment with mirtazapine in persons with sNVP is available. For persons treated until delivery, maternal and cord blood will be obtained for plasma mirtazapine concentration measurement to evaluate placental transfer. If postpartum mirtazapine treatment is desired, it will be coordinated with our Collaborative Care Perinatal Services (COMPASS - the integrated mental health program in the Obstetrics department), or in the Asher Center in the Department of Psychiatry, which [name] directs.

Figure 4: Data Collection: Continuation Treatment					
Maintenance (every 4 weeks)	Delivery				
Wt, Ht, BP PUQE GH Plasma PHQ-9 GAD-7 C-SSRS ASE SS Medication Log	PES Maternal and umbilical cord blood				
Log PUQE=Pregnancy Unique Quality of Emesis; PHQ-9=Patient Health Questionnaire; GAD-7 =Generalized Anxiety Disorder; C-SSRS=Columbia-Suicide Severity Rating Scale; ASE=Asberg Side Effects; SS=Screen for Serotonin Syndrome. PES, Peripartum Events Scale.					

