9-Item Patient Health Questionnaire (PHQ-9)⁶⁰: The 9-Item Patient Health Questionnaire (PHQ-9) is a self-administered instrument based on the nine DSM-5 criteria listed under criterion A for Major Depressive Disorder. The questionnaire includes criteria based diagnosis of depressive symptoms, assists in identifying treatment goals, determining severity of symptoms, as well as guiding clinical intervention. When considering a diagnosis, the clinician will use clinical interviewing skills to determine whether the symptoms are causing clinically significant distress or impairment and those symptoms are not better explained or attributed to other conditions, such as substance use, medical conditions, or bereavement.

Generalized Anxiety Disorder Scale, **7-item (GAD-7)**⁶¹**:** The Generalized Anxiety Scale is a 7-item self-report for symptoms consistent with the Diagnostic and Statistical Manual of Mental Disorders of generalized anxiety disorder.

Peripartum Events Scale (PES)⁶²: The Peripartum Events Scale (PES) captures data from several categories in the birth record. The following categories of events are included: medical and obstetric risk factors, time in operating room, fetal monitoring, surgical complications, infant anthropometrics and outcome, NICU admission, and postpartum complications (such as infection, hemorrhage). Admission to the special care nursery will also

be noted. We have modified the original measure to align with current obstetrical practices. The PES will be completed for all enrolled participants.

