were observed in the newborns of 26 women exposed to mirtazapine in the first trimester. Of 54 infants exposed in the third trimester, 14 (26%) had poor neonatal adaptation, similar to the rate observed after SSRI exposure. Birth weights were within the normal range. Preterm births occurred in 9% of exposed newborns vs. 7.7% of the general population. In summary, although the total number of women with first-trimester exposure to mirtazapine is relatively small (N=487), the results do not suggest a signal for birth defects. The majority of large-scale studies of populations of women who have taken antidepressant medications similar to mirtazapine, neither birth defects nor neurodevelopmental problems (including autism⁷⁰) have been associated with the use of these drugs⁷¹. Additional data on pregnancy and newborn outcomes associated with mirtazapine exposure in the context of sNVP will be obtained in the proposed R21 study and included in the later Phase 3 RCT, if such a trial is supported by data from this R21 study.

Pharmacotherapy with any drug for NVP is associated with benefits and harms that must be balanced by the physician and patient. Commonly used drugs, such as ondansetron, metoclopramide, and prochlorperazine also have treatment benefits and harms that must be balanced against the risks associated with sNVP. Ondansetron use increased from less than 1% prior to 2000 to 13% in 2014.⁷² Data from the National Birth Defects Prevention and Slone Birth Defects Studies showed that ondansetron exposure was not associated with an elevated risk for the majority of defects; however, increased risks were observed for cleft palate (adjusted OR=1.6, 95% CI 1.1-2.3) and renal agenesis-dysgenesis (OR=1.8, 95% CI 1.1-3.0) in the Birth Defects Study.⁷² Huybrechts et al ⁷³ evaluated 1,816,414 pregnancies with 88,467 (4.9%) and reported that first-trimester exposure to ondansetron was not associated with overall congenital or cardiac malformations but with a small increased risk of oral clefts (RR=1.24 (95% CI, 1.03-1.48).

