We will evaluate the potential need for change in the dosing for the subsequent RCT by balancing the time to response against the emergence of any side effects. For example, if the 15 mg/day dose is well tolerated but the major symptom reduction occurs at 30 mg/day, we will consider the advisability of a more assertive dosing regimen with our DSMB and FDA consultants.

Aim 3. The drug tapering strategy will be assessed by evaluating the emergence of somatic symptoms on the Asberg side effects profile during the taper. Obtaining weekly plasma concentrations in the initial 21-day trial allows an exploration of whether a relationship between mirtazapine concentration and antinauseant/ antiemetic efficacy is likely in this group of women. The patient's genotypes and corresponding phenotypes (ultrarapid, rapid, intermediate, poor metabolizers--by specific enzyme) will be evaluated for their relationship to plasma mirtazapine concentrations. Biotransformation is mediated by CYP2D6, CYP3A4, and 1A2.²

Aim 4. Evaluate the maternal and fetal safety of mirtazapine. The maternal and neonatal outcomes from the PES will be reviewed for consistently reported events across subjects. We will compare the mirtazapine exposure data to that of women who have taken SSRI through pregnancy in our Obstetric-Fetal Pharmacology U54 study (N=88), Optimizing Medication Management for Mothers with Depression. Neonatologist [name] (see letter of support) will collaborate with our team to interpret the OPTI-MOM neonatal outcome data from the PES in the proposed trial (fetal exposure to mirtazapine) and compare it with the PES from our current OPTI-MOM subjects (fetal exposure to SSRI antidepressants). We have used these measures in our studies of SSRI exposure on neonates.³ The PES includes medical and obstetric risk factors, time in the delivery/ operating room, fetal monitoring, surgical complications, infant anthropometrics, special care/NICU admission, and post-birth complications. We will compare data using t-tests, chi-square test, and nonparametric tests as appropriate according to the type of data and their distributions.

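### SAP Aim 4 pools all mirtazapine exposure and compares it with SSRI use throughout pregnancy, which dilutes outcomes that depend on when the fetus was exposed

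*Protocol*

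**What the plan says.** **Population and analysis.** The protocol's Objectives section states Aim 4 as "Determine pregnancy and neonatal outcomes for all enrolled persons", and the description of the Peripartum Events Scale (PES) adds "The PES will be completed for all enrolled participants". SAP Aim 4 then plans as follows: "The maternal and neonatal outcomes from the PES will be reviewed for consistently reported events across subjects". It continues: "We will compare the mirtazapine exposure data to that of women who have taken SSRI through pregnancy". That comparator is a cohort of 88, and the tools are t-tests, chi-square and nonparametric tests. Item 9 of the DSMB review list in the protocol plans the same kind of comparison with in-utero SSRI exposure. Neither document gives a denominator by time of exposure.

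**Timing of exposure.** Figure 6 sets no gestational-age limit. The definition of severe disease in the Objectives section includes symptoms that persist past 20 weeks, while the compensation section foresees entry at 5 weeks. After the three-week trial a woman may taper or continue. For those who continue, "The duration of treatment will be decided by the patient with a study obstetrician based upon her response and comfort with drug discontinuation" (Maintenance Drug Treatment). Cord blood is planned only for women treated up to delivery.

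**The protocol's own evidence.** Under Reproductive Exposure Data, two outcomes are tied to a window. For late exposure, "Of 54 infants exposed in the third trimester, 14 (26%) had poor neonatal adaptation". For early exposure, "although the total number of women with first-trimester exposure to mirtazapine is relatively small (N=487), the results do not suggest a signal for birth defects".

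**The concern.** A woman who takes the drug for a few weeks early in pregnancy and stops cannot show an effect of late exposure on her newborn. A woman who starts after the first trimester cannot show a first-trimester effect. Under the plan both stay in the denominator for every outcome. If a harm arises only from exposure in one window, the pooled rate is a mixture of exposed and unexposed pregnancies and lies closer to the unexposed rate.

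The comparator adds to this. The SSRI women are described as exposed throughout pregnancy, so on late-exposure outcomes a fully exposed group is set against a partly exposed one. That mismatch works in mirtazapine's favour. Fetal safety is a stated aim, and the protocol says these data will feed the decision on a phase 3 trial and be added to the existing exposure evidence. A pooled count cannot be set beside that evidence on the same footing.

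**Working it through.** **Inputs from the documents**
- Late-exposure risk: 14 of 54 (protocol, Reproductive Exposure Data).
- Planned N: 25; comparator: 88; enrolled before closure: 2 (SAP).
- Cited series of seven cases: mean start 11.6 weeks (range 7–14), mean duration 9.1 weeks (range 4–24) (protocol, Background).

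**Assumptions, not in the documents**
- *k*, the number of the 25 exposed in the relevant window: 3 to 25 shown.
- *b*, the event rate without exposure in the window: 0, 5% and 10% shown.

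**1. The plan's own figures.** 14/54 = 25.9%, which matches the stated 26% (exact 95% interval 15.0% to 39.7%). 104 + 357 + 26 = 487, which matches the first-trimester total. 20/(1 − 0.20) = 25, which matches the enrolment target.

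**2. Does exposure timing vary?** In the cited series the means give 11.6 + 9.1 = 20.7 weeks as an average stop. The extremes allow stops from 7 + 4 = 11 to 14 + 24 = 38 weeks. Some women may therefore have no late exposure and others may have it. The series does not settle the split.

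**3. Dilution.** Pooled rate = [k × 14/54 + (25 − k) × b] / 25.

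| k | b = 0 | b = 5% | b = 10% |
|---|---|---|---|
| 25 | 25.9% | 25.9% | 25.9% |
| 12 | 12.4% | 15.0% | 17.6% |
| 5 | 5.2% | 9.2% | 13.2% |
| 3 | 3.1% | 7.5% | 11.9% |

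**4. Effect on the SSRI comparison.** The protocol calls the 26% similar to the rate seen after SSRI exposure. Suppose both drugs carry 25.9% in late-exposed infants and the SSRI group is all late-exposed. With b = 5%, the pooled comparison shows a gap in mirtazapine's favour of 25.9 − 15.0 = 10.9 points (k = 12) or 25.9 − 9.2 = 16.7 points (k = 5), where the true difference among exposed infants is nil. Across b = 0 to 10% the gap is 13.5 to 8.3 points for k = 12 and 20.7 to 12.7 points for k = 5.

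**5. Zero events.** Two-sided exact 95% upper limit = 1 − 0.025^(1/n). Chance of no events at a risk of 14/54 = (40/54)^n.

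| n in the denominator | Upper limit | Chance of zero events |
|---|---|---|
| 25 | 13.7% | below 0.1% |
| 10 | 30.8% | 5.0% |
| 5 | 52.2% | 22.3% |
| 2 | 84.2% | 54.9% |

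On 25 the limit lies below 26%. On 10 or 5 it does not.

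**The case against.** **Enrolment closed at 2.** The SAP says so, and the figures for 25 describe a cohort that was not recruited. With two women no one would read a zero count as reassurance. This stands, and it limits the practical effect to how those two are reported and to what is carried into phase 3.

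**Neonatal adaptation and malformation are not named among the PES categories.** This also stands. The 26% serves here only as a worked example. The outcome in the PES list most plainly open to a late-exposure effect is special care or NICU admission; malformations would come in only through the infant-outcome item.

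**Much of the cited evidence has no window.** Birth weight, preterm birth and miscarriage are reported without one. A reader might infer that every Aim 4 outcome is diluted; the documents do not support that.

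**The SAP has no zero-count rule and disclaims power.** A reader might infer that the plan would declare safety from few events, or that it counts only events seen in every subject. It says neither: the phrase about consistently reported events is more naturally read as a search for recurrent ones. The power disclaimer does not answer the point, however, because the wrong denominator shifts the estimate and does not merely widen it.

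**Timing is recorded, and a neonatologist interprets the outcomes.** At this size, case review could allow for timing. The SAP does not say that it will, and the planned tests on one pooled group do not.

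**The late-exposed women are a selected group.** They have continuing pregnancies and probably persistent symptoms, and the protocol links severe disease itself to preterm birth and small newborns. This is a real limit on the remedy and the reason to label the comparison descriptive.

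**Conclusion.** The point holds for window-dependent outcomes: late-exposure neonatal outcomes such as special care or NICU admission, and malformations if they are captured. For these, the pooled analysis pulls the rate toward the unexposed rate, and the mismatch with an SSRI group exposed throughout pregnancy favours mirtazapine. That direction follows from the design, provided the harm is confined to the window and some enrolled women fall outside it. It describes this one source of bias; confounding by disease severity could push the overall comparison either way.

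The size is not determined, because *k* and *b* are assumptions. A reader might infer from the 20.7-week average that most women would be unexposed at delivery. Seven cases with durations of up to 24 weeks do not support that, and the protocol itself says that no information on duration in this condition is available. Nor do starts at 7 to 14 weeks in that series suggest much dilution for first-trimester exposure; that half of the point rests on the absence of a gestational-age limit.

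**What to change.** In SAP Aim 4 and item 9 of the DSMB review list:

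1. Keep the summary of all enrolled women. Leave the outcomes that the protocol reports without a window (birth weight, preterm birth, miscarriage) on that basis.
2. Add one table of the window-dependent outcomes by exposure: first trimester yes/no, and third trimester or delivery yes/no. Derive the windows from gestational age at first dose and the Medication Log. Give counts, denominators and exact intervals, and base any statement about a window on the women exposed in it.
3. For late-exposure outcomes, make the SSRI comparison with the late-exposed women and label it descriptive.
4. State whether malformations are recorded under the infant-outcome item of the PES; if not, leave them out of the table.

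**Cost.** One table, with no new data: gestational age is on the screening list and the log is kept throughout. Cells will be very small (0 to 2 given actual enrolment) and intervals wide, which is the precision the data have. The late-exposed subset is selected on persistent symptoms and continuing pregnancy, and the report should say so next to the table.

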Mirtazapine provides nausea control with once-daily dosing³² and is available as an orally disintegrating tablet. Ondansetron, prochlorperazine and metoclopramide require multiple daily doses. In patients with cancer, mirtazapine (15-30 mg) rapidly improved nausea, appetite, insomnia and overall function.³³ Mirtazapine also is effective in preventing post-anesthesia NV. People scheduled for gynecological surgery were randomly assigned to mirtazapine 30 mg plus dexamethasone vs. dexamethasone alone. The rate of post-operative NV was 20% vs. 50%, respectively (P< 0.01).² In a meta-analysis, mirtazapine significantly reduced post-operative NV vs. placebo (risk ratio=0.44; 95% CI 0.32--0.62).³⁴ For the first time, mirtazapine was identified as an option for sNVP by obstetricians in a review published in 2020.³⁵

Mirtazapine is well-absorbed with or without food and peak plasma concentrations are reached in 1 to 2 hours. Hepatic cytochrome P450 (CYP) 2D6 and 1A2 enzymes contribute to the formation of the 8-hydroxy metabolite, which has 10% of the parent drug's activity. CYP3A4 is responsible for subsequent metabolism. Mirtazapine is a weak inhibitor of CYP450 enzymes and is unlikely to result in significant drug interactions.³⁰

[figure not shown]
Variability in pharmacokinetics is associated with variation in genes encoding drug-metabolizing enzymes involved in drug elimination or biotransformation. Mirtazapine is primarily metabolized by CYP2D6, which has important genetic polymorphisms^{36,37} that influence drug clearance and plasma concentrations. The activity of CYP2D6 varies across pregnancy by genotype. CYP2D6 substrate drug levels decline in rapid and extensive metabolizers and increase in intermediate and poor metabolizers.³⁸ Genotypes that determine the activities of CYP2D6, and minor pathways 3A4/5 and 1A2, will be explored for associations with mirtazapine plasma

concentrations. Genotypes that increase risk for HG will also be determined. In a genome-wide association study for binary (HG) and ordinal (severity of nausea and vomiting) phenotypes of pregnancy complications, two loci, chr19p13.11 and chr4q12, were genome-wide significant ($p < 5 \times 10-8$) and replicated in an independent cohort.³⁹ The genes implicated at these two loci are GDF15 and IGFBP7 respectively, both known to be involved in placentation, appetite, and cachexia.

These analyses will be exploratory due to the limited sample size achievable in an R21 study.

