Physiology of Emesis. Vomiting is a complex neuromuscular cascade of events coordinated by the central and autonomic nervous systems.⁴⁰ Neurons that orchestrate emesis are located throughout the medulla and organized by a central pattern generator (CPG) that coordinates the sequence of events leading to emesis. The CPG receives input from the area postrema and abdominal vagal afferents. Anti-emetic drugs antagonize neurotransmitters (Figure 1⁴⁰) that orchestrate the progression of nausea to vomiting. Commonly used anti-emetics antagonize the following receptors: muscarinic acetylcholine (mR), dopamine (D_2) , serotonin (5-HT₃), histamine (H_1) and neurokinin (NK_1) . Both ondansetron and mirtazapine are serotonin (5HT₃) receptor antagonists⁴⁰ which prevent vagal afferent signaling to the hindbrain; however, mirtazapine offers three additional sites of action to impede the emetic process (Figure 1⁴⁰): 1) histamine (H_1R) , which has input directly to the vomiting center; 2) muscarinic (mR) which also has input directly into the vomiting center; and 3) central presynaptic adrenergic α_2 (adrenergic $\alpha_2 R$), which activates emesis.

Figure 1. Neurotransmitters involved in emesis and sites of action: $\alpha_2 \mathbf{R}$ =adrenergic α_2 -receptor; CPG=central pattern generator; $D_2 \mathbf{R}$ =dopamine 2receptor; Δ^9 -THC= Δ 9-tetra-hydrocannabinol; DVC=dorsal vagal complex; **5-HT**=serotonin; **H**=histamine; NK=neurokinin; **m**R=muscarinic; mirtazapine's action indicated by arrows at receptor sites that are bolded below and arrows are receptor site.

STUDY ENDPOINTS:

The primary outcome is the change in PUQE (Pregnancy Unique Quality of Emesis)⁴³ score. Secondary outcomes include: (1) Self-administered Comorbidity Questionnaire, (2) NIH PROMIS Global Health scale, (3) Patient Health Questionnaire-9 (depression scale), (4) Generalized Anxiety Disorder-7 scale, (5) Asberg Side Effects. Plasma will be obtained for quantitation of mirtazapine concentrations at each assessment during mirtazapine treatment. DNA will be obtained to explore whether pregnant persons who are most (or least) likely to benefit from treatment can be identified through pharmacogenetics.

STUDY INTERVENTION(S) / INVESTIGATIONAL AGENT(S):

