Authorized research personnel will work with clinicians from the Northwestern Obstetrics and Gynecology services and the Obstetrical Triage program to identify potentially eligible individuals and approach them about their interest in participating. We have defined several eligibility criteria to allow participants to be screened by our study team. Subject burden can be reduced and study efficiency improved by asking only those subjects likely to be eligible to undergo a full baseline assessment. The screen includes: 1) age 2) gestational age of the fetus, 3) confirmation of plan to receive care and deliver at Prentice Women's Hospital (PWH), 4)

PUQE score of 10-15, 5) has been treated with at least two anti-emetic/antinauseant drugs with inadequate response; and 8) English speaking.

The inclusion/exclusion criteria will be reviewed in the patient's chart and documented on the screening log. If a patient meets all the inclusion criteria for enrollment, does not have any of the exclusion criteria, she will be approached about the study by authorized personnel. Her primary obstetrician will be contacted to review the patient's participation.

Brochures will be available to provide potential subjects with additional information. We will also post information about this study on our Asher Center and Northwestern Medicine websites, as well as post on the NCT site.

COMPENSATION FOR PARTICIPATION IN RESEARCH ACTIVITIES

Participants will be compensated with \$35 for each week of the three-week trial. If a participant wishes to participate in the continuation period or a mirtazapine tapering regimen, they will continue for 5 additional weeks and compensated with \$35 each week.

If a participant enters into the study early in pregnancy (gestational age of 5 weeks), they will have monthly visits after the 8 weeks is completed, for a maximum total of 10 visits.

Compensation will be provided in a form of a check at the end of each week during their followup visit.

WITHDRAWAL OF PARTICIPANTS

A participant will be withdrawn from the research without their consent if there is: 1) refusal to follow the medication protocol, and/or 2) refusal to answer study questionnaires, 3) the participant fails to respond to contact attempts from the study team.

RISKS TO PARTICIPANTS

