In a large retrospective cohort study, infants exposed to metoclopramide in the first trimester were compared to unexposed infants. No significant differences in congenital malformations, birth weight, preterm delivery or perinatal death were observed.⁷⁴ Although data for prochlorperazine are limited¹⁴, no consistent evidence of teratogenesis exists for the use of phenothiazine drugs in the treatment of NVP. Chronic maternal use of metoclopramide and prochlorperazine increase the risk for maternal extrapyramidal movement disorders and neonates have experienced agitation, hyper- or hypotonia, tremor, somnolence and respiratory distress.

Blood sampling will be done to allow the plasma assay for mirtazapine concentrations. The phlebotomy services will be obtained from the Diagnostic and Treatment Center on the second floor of Arkes Pavilion, Prentice Women's laboratory services, or the Asher Center clinical research laboratory. All are accessible through indoor walkways from Prentice Women's Hospital. There are minimal risks to phlebotomy, which are rare and include bruising, pain, infection and mild maternal anxiety. The amount of blood that will be drawn at enrollment for study purposes is 3 ml (thyroid hormones) and 5 ml (DNA sample), for a total of 8 ml, and 5 ml at each follow up assessment for plasma concentrations of mirtazapine.

POTENTIAL BENEFITS TO PARTICIPANTS

There is no definitive benefit to participants from whom data will be collected. Pregnant persons may benefit from the additional education about the disorder and possibly from treatment with the promising drug mirtazapine. The additional monitoring by study staff may be perceived as supportive.

The dearth of information about the treatment of sNVP has been identified in systematic reviews, meta-analyses and the recent NICHD-led Task Force on Research Specific to Pregnant Women and Lactating Women (PRGLAC). Data to inform the acceptability, tolerability, dosing and design of a subsequent randomized controlled trial to expand pharmacotherapy would be a major contribution in the care of pregnant persons.

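### The Protocol's risks section draws the DNA sample at enrollment, but Figure 3 schedules it at Day 7, so women who leave before Day 7 could have no genotype

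*Protocol*

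**What the plan says.** **Timing in the text.** The Protocol, RISKS TO PARTICIPANTS (blood sampling), states: "The amount of blood that will be drawn at enrollment for study purposes is 3 ml (thyroid hormones) and 5 ml (DNA sample". It totals these at 8 ml and then gives "5 ml at each follow up assessment for plasma concentrations of mirtazapine". DNA is not mentioned at follow-up.

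**Timing in the schedule.** Figure 3 (PROCEDURES INVOLVED) has one row for research blood. Its intake cell is empty. DNA appears with plasma at the Day 7 visit, and plasma alone appears at Days 14 and 21. Figure 4, for the continuation phase, lists plasma but no DNA.

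**Use of the sample.**
- STUDY ENDPOINTS: "DNA will be obtained to explore whether pregnant persons who are most (or least) likely to benefit from treatment can be identified through pharmacogenetics".
- OBJECTIVES, aim 5: "Explore the relationship of study drug dose and plasma concentration with side effects and pharmacogenetics by obtaining weekly plasma".
- DATA AND SPECIMEN BANKING: the serial concentrations are to be related to tolerability, side effects, adverse events and pharmacogenetic data.
- BACKGROUND: genotypes linked to the risk of hyperemesis gravidarum (HG) will also be determined. It says of the genetic work: "These analyses will be exploratory due to the limited sample size achievable in an R21 study".
- SAP, Aim 3: genotypes and metabolizer phenotypes "will be evaluated for their relationship to plasma mirtazapine concentrations".

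**The concern.** Treatment does not change a germline genotype, so a draw after a week on drug gains nothing. It does make having a genotype depend on still being in the study at Day 7.

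The Protocol's BACKGROUND argues that pharmacogenetic factors alter mirtazapine concentrations and, through them, tolerability. It adds that levels of CYP2D6 substrates rise during pregnancy in intermediate and poor metabolizers. On that reasoning, leaving early because of side effects could be related to genotype. Genotypes missing for that reason would not be missing at random in an analysis asking who tolerates or benefits from the drug.

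The schedule may also outlast this study. The Protocol says the final manual of operating procedures should hold what is needed to construct the later definitive trial, so an unresolved conflict could be carried into it.

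**Working it through.** **1. Does Figure 3 really say Day 7?** The figure was read from PDF, so the columns were checked by setting the cells of the blood row against the day header. The weight and blood pressure row served as a control.

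| Row | Intake/Day 1 | Day 7 | Day 14 | Day 21 |
|---|---|---|---|---|
| Blood | empty | DNA, plasma | plasma | plasma |
| Weight/BP (control) | weight, height, BP | weight, BP | weight, BP | weight, BP |

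The control row falls where it should, so the Day 7 reading of DNA is sound.

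**2. Does another section settle it?** No. The enrollment paragraph under PROCEDURES INVOLVED lists a blood count, metabolic screen and urinalysis without DNA. It also omits the thyroid sample that the risks section places at enrollment, so it is not a full inventory of draws and cannot decide the matter. The endpoint, specimen-banking and SAP texts give no draw time.

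**3. Blood volumes (ml), from the risks section.**
- Text schedule: enrollment 3 + 5 = 8; Days 7, 14 and 21 at 5 each; total 8 + 5 + 5 + 5 = 23.
- Figure 3 schedule, same tubes: enrollment 3; Day 7 5 + 5 = 10; Days 14 and 21 at 5 each; total 3 + 10 + 5 + 5 = 23.

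The three-week total is the same. Only the visit at which 5 ml is taken differs.

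**4. Can a woman leave before Day 7?** Yes, by several routes.
- WITHDRAWAL OF PARTICIPANTS lists "refusal to follow the medication protocol", refusal of questionnaires and failure to respond to contact.
- TRIAL STOPPING CRITERIA ends an individual's participation for, among other things, a Grade 3 or higher drug-related serious adverse event.
- On treatment itself the Protocol says: "Mirtazapine treatment will continue unless the participant withdraws consent, experiences a limiting side effect". It does not say whether a woman who stops the drug still attends Day 7.

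The day 2 side-effect contact is by telephone or telehealth, so it yields no sample. No early-termination visit or alternative DNA draw is described.

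**5. How many genotypes could be lost?** SAP, Sample Size Considerations: 20 / (1 − 0.20) = 25, which reproduces the planned enrollment. The allowance is 25 × 0.20 = 5 dropouts. Assuming dropout equals that allowance:
- if all five still give DNA at Day 7, 0/25 = 0% are lost;
- if all five leave before Day 7, 5/25 = 20% are lost.

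The documents give nothing to place the figure within that range.

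**6. Which analyses are exposed?** A woman who leaves before Day 7 has no plasma sample under either schedule. She contributes nothing to genotype against concentration, or to any model that works through concentration, wherever DNA is drawn. The timing matters for direct comparisons of genotype with benefit, side effects or tolerability, and for the HG-risk genotypes.

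**The case against.** The best defence is that this is a mismatch between text and figure with little consequence. The risks section already states the better schedule. A limiting side effect ends treatment, not necessarily participation: delivery outcomes are wanted for everyone enrolled, and eligibility is tied to one hospital's practices to keep women in the study through pregnancy. Because genotype is fixed, a missed tube could be drawn at a later contact. The genetic analyses are declared exploratory, and the one the SAP specifies is tied to plasma. The SAP also reports that only 2 women enrolled before closure and that both completed the three weeks, so neither left before Day 7.

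Most of this stands and limits the point. It does not remove the contradiction. A later draw is possible in principle but is not scheduled anywhere, including Figure 4.

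Three stronger readings are tempting, and the documents do not support them:
- **Every woman who cannot tolerate week 1 loses her genotype.** One who has side effects, or even stops the drug, but attends Day 7 still gives DNA.
- **All the losses would be for intolerance.** The 20% is a general dropout allowance. It is not split by reason, and the exit routes include withdrawn consent and lost contact.
- **The missingness biases associations toward no effect and under-counts slow metabolizers.** This is plausible from the protocol's pharmacology but not shown. No passage links genotype to stopping in the first week.

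**Conclusion.** The conflict is real and unresolved, and the two places must be reconciled. If Figure 3 is followed, between 0 and 5 of the planned 25 women would have no genotype, with some possibly missing for reasons related to tolerability. That range assumes total dropout equal to the plan's 20% allowance and no DNA collection outside the schedule.

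The effect is confined to exploratory genotype comparisons that do not need a plasma sample. The SAP's genotype-by-concentration analysis is little affected, and the primary outcome and sample size are untouched. It is a modest point, worth correcting because the loss is avoidable at almost no cost.

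**What to change.** In Figure 3, move DNA from the Day 7 column to the intake column, before the first dose, so that it agrees with the risks section. Leave plasma alone at Days 7, 14 and 21. Add DNA to the enrollment procedures so that all three places agree.

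State in the SAP that any exploratory summary of genotype against side effects or benefit includes women who leave before Day 7. The SAP does not now specify such a summary, so this sentence governs one if it is done and does not require it.

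The cost is one table cell and two sentences. The tubes and the 23 ml three-week total do not change, and the sample is taken with blood already drawn at enrollment. The downside is a few DNA samples from women who enroll but never take a dose.
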